### 17.4.4 Examination of changes in tumor biomarkers after one cycle of initial treatment

For each treatment arm, a Spearman rank correlation coefficient will be used to examine the association of maximum percentage of tumor shrinkage during treatment with the percent change after 1 cycle of treatment in AAK expressing cells, as well as percent changes after 1 cycle of treatment in tissue ER $\alpha$ , SMAD5, SOX2 expression and phosphorylation.

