### 2.3 Correlative Research

- 2.3.1 To assess the changes in Aurora A kinase, SMAD5 and SOX2 expression and phosphorylation in tumor tissue after first cycle of assigned treatment
- 2.3.2 To assess the changes in ER expression and function in tumor tissue after the first cycle of assigned treatment

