### 9.1.2 Methods

#### Circulating Tumor Cell Capture and Phenotyping

The relative abundance of CTCs in the peripheral blood has strong correlation with tumor recurrence and distant metastases in both early stage and advanced breast tumors. We will prospectively isolate CTCs from blood specimens collected from study participants at three time points for phenotypic and possibly genotypic analyses.

One 10 mL blood sample will be collected in the CellSave® Preservation Tube for CTC isolation using the Veridex CellSearch™ system (Janssen; Raritan, NJ). CellSave® contains an optimized preservative that stabilizes cells for up to 96 hours at room temperature. The CellSearch™ system [REDACTED] allows for the

immunomagnetic selection, fluorescence staining, concentration, and enrichment of CTCs for enumeration and analysis. The FDA cleared process uses the CellSearch™ Epithelial Cell Kit, which contains anti-EpCAM (epithelial cell adhesion molecule) Ferrofluid, a fluorescent nucleic acid dye (DAPI), and fluorescently labeled monoclonal antibodies specific for leukocytes (CD45) and epithelial cells (cytokeratins 8, 18, and 19) to identify CTCs as those that are cytokeratin positive, DAPI positive, and CD45 negative with the appropriate morphology. At least two-thirds of patients with metastatic breast cancer have >1 CTC per 7.5 mL blood assayed with this technology, and the enumeration of CTCs relative to a threshold of 5 CTCs per 7.5 mL blood is associated with clinical outcomes in this patient population. The standard process has been modified to allow for CTC retrieval and subsequent assessment for additional protein markers of interest (e.g., Aurora A kinase, ER, p-SMAD5, and p-SOX2).

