#### 9.2.2.3 Aurora A Kinase, SMAD5, SOX2 and ER $\alpha$ Expression

Antibodies to detect total Aurora-A kinase, ER $\alpha$ , SMAD5 and SOX2, and phospho-SMAD5 and phospho-SOX2, are available through the Mayo PRC or will be purchased from Cell Signaling Technology, Boston, MA, USA and processed according to package insert. The phospho antibodies will be optimized through standard procedure with the PRC. Normal human breast tissues from reduction mammoplasty will serve as negative control and triple-negative breast tumor tissues as positive control. The intensity of biomarkers expression will be scored as strong, moderate, or weak-to-none using digital image analysis employing an innovative *ImageScope viewing software (Leica Biosystems)* to accurately measure Aurora-A, SMAD5, SOX2 and ER $\alpha$  nuclear expression in breast tumor clinical samples.

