### 17.3 Stratification Factors

This study will use the Pocock and Simon dynamic allocation procedure to allocate an equal number of patients to each of the treatment strategies. This procedure will balance the marginal distributions of the stratification factors, clinical endocrine resistance and ER status, between these treatment strategies.

- Clinical Resistance to Endocrine Therapy:
  - 1= Primary endocrine resistance- recurrence within the first 2 years of adjuvant endocrine therapy, or progression within the first 6 months of initiating first-line endocrine therapy for MBC
  - 2= Secondary endocrine resistance- recurrence during Years 2-5 of adjuvant endocrine therapy (or within 12 months of completing adjuvant endocrine therapy) or progression occurring 6 or more months after initiating endocrine therapy for MBC.
- ER findings from registration biopsy
  - 1 = ER positive ( $\geq 10\%$  staining)
  - 2 = ER weakly positive (1 to 9.9% staining) or ER negative (0% staining)
- Prior therapy with a CDK 4/6 inhibitor (palbociclib, ribociclib or abemaciclib)
  - 1=yes

2=no

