### 17.4.5 Examination of changes in blood biomarkers after one cycle of initial treatment

At the end of Cycle 1, the percent change in CTC expression of Aurora A kinase, ER, and phospho- SOX2 expression from pre-treatment levels will be determined for each patient.

Bland-Altman plots and weighted kappa statistics will be used to examine the concordance between the percent change in Aurora A kinase, ER, and phospho-SOX2 expression from pre-treatment levels in CTC and in tumor tissue.

A plot of the percent change expression of Aurora A kinase, ER, and phospho-SOX2 expression from pre-treatment levels in CTCs and that in tissue will be constructed with using different symbols for each type of clinical response (CR, PR, SD or PD) to visually assess for trends.

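### Marker change is analysed as percent change, which has no value at 0% baseline ER, and no analysis estimates or tests whether tissue expression changes after Cycle 1

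*Combined protocol and SAP*

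**What the plan says.** The tissue analysis is in Section 17.4.4: "For each treatment arm, a Spearman rank correlation coefficient will be used to examine the association of maximum percentage of tumor shrinkage during treatment", with percent change in Aurora A kinase-expressing cells and "percent changes after 1 cycle of treatment in tissue ER"α, SMAD5 and SOX2 (expression and phosphorylation). Section 17.4.5 takes "the percent change in CTC expression of Aurora A kinase, ER, and phospho- SOX2 expression from pre-treatment levels" and compares it with tissue by Bland-Altman plots and weighted kappa.

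Section 17.3 pools ER staining of 0% and of 1 to 9.9% into one stratification level. Section 1 explains that ER-negative patients are enrolled because alisertib may restore ER.

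Objective 2.3.2 is "To assess the changes in ER expression and function in tumor tissue after the first cycle of assigned treatment". Objective 2.3.1 asks the same for Aurora A kinase, SMAD5 and SOX2. On the assay, Section 9.2.2.3 states: "The intensity of biomarkers expression will be scored as strong, moderate, or weak-to-none". The same sentence says that this is done by digital image analysis.

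**The concern.** Percent change divides by the baseline value. A patient at 0% ER has no value, and a patient at 1 to 9.9% can show a very large value for a small gain. Section 17 gives no rule for a zero baseline, no offset and no absolute-change alternative. The patients affected belong to the stratum that was admitted to examine ER restoration.

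A second gap does not depend on the measure. Correlating change with shrinkage does not show whether expression changed. ER could rise by the same amount in every patient and the correlation would show nothing. The correlative objectives would then have no result, although the paired biopsies were taken.

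**Working it through.** **The plan's nearest stated figure.** Section 17.4.4 gives no power. Section 17.4.3 gives 90% for a baseline Spearman test (n = 81, two-sided alpha 0.05, correlation 0.35). By Fisher z, power = Φ(atanh(0.35) × √78 − 1.96) = Φ(3.23 − 1.96) = 89.8%, which agrees. With the Spearman variance 1.06/(n − 3) it is 88.0%.

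**Patients affected.** Inputs: 45 per arm (17.2); 90% with usable baseline tissue (17.4.3); 10% ER-negative (Section 1); up to 20% with ER <10% or negative (3.5).
- Usable per arm: 0.9 × 45 = 40.5.
- At 10%: 4.05 per arm, about 8 in total. At 20%: 8.1 per arm, about 16 in total.
- The split between 0% and 1 to 9.9% is not given, so anywhere from none to all of these have no value. If all do, 36.45 or 32.4 per arm remain.

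Paired tissue at the end of Cycle 1 could be scarcer; the plan gives no figure for it.

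**Dependence on baseline.** Percent change = 100 × (post − baseline)/baseline.

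| Baseline → post | Points | Percent change |
|---|---|---|
| 0 → 20 | +20 | undefined |
| 1 → 2 | +1 | +100% |
| 1 → 20 | +19 | +1900% |
| 50 → 65 | +15 | +30% |
| 90 → 100 | +10 | +11% |

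The largest possible rise is +9900% from 1%, +100% from 50% and +11% from 90%.

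**Effect on the rank correlation (17.4.4).** Per-arm power at correlation 0.35 (variance 1.06/(n − 3)) is 58% at n = 40, 53% at n = 36 and 48% at n = 32.

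A simulation assumed 40 patients per arm and a latent correlation of 0.5. ER <10% patients were 10% or 20%, with half or all of them at 0%. Their mean ER rise was 0 or 20 points, with shrinkage moving in step. Mean Spearman correlations with the 20-point rise were:

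| ER <10% share | Of these at 0% | Percent change | Absolute, same patients | Absolute, all patients |
|---|---|---|---|---|
| 10% | half | 0.457 | 0.483 | 0.508 |
| 10% | all | 0.429 | 0.453 | 0.508 |
| 20% | half | 0.489 | 0.515 | 0.552 |
| 20% | all | 0.432 | 0.458 | 0.552 |

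Re-ranking costs about 0.02 to 0.03 (column 4 minus column 3). Losing the 0% patients costs 0.025 to 0.094 (column 5 minus column 4). With no rise, the total gap between percent change and absolute change is only 0.01 to 0.02.

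**Effect on Bland-Altman limits (17.4.5).** As an illustration, take 40 tissue-minus-CTC differences, 39 of them zero and one d = +1900. The mean is d/40 = 47.5 and the SD is d/√40 = 300.4. The limits are 47.5 ± 1.96 × 300.4, or −541 to +636 percent, although 39 of 40 patients agree perfectly. In points (d = 19) they are −5.4 to +6.4.

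**Objectives against analyses.** Section 17.4.3 correlates markers at baseline and tests whether weak or absent phosphorylated AURKA, SMAD5 and SOX2 after one cycle is associated with clinical benefit. Section 17.4.4 correlates change with shrinkage. Section 17.4.5 assesses agreement between CTC and tissue changes. None estimates or tests within-patient change in tissue. Objective 2.3.2 also names ER function; the PCR of ER target genes in 9.2.2.2 has no analysis in Section 17.

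**The case against.** Several stronger readings are tempting, and the documents do not support them.

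- *Extreme values wreck the tissue analysis.* Section 17.4.4 is rank-based, so +1900% is only a high rank. The loss is modest, as shown above.
- *Up to 18 of 90 patients have no value.* The 20% in Section 3.5 covers all ER below 10%, including 1 to 9.9%, where percent change is defined.
- *The patients in whom restoration can be seen are excluded.* Patients at 1 to 9.9% keep a value. On the plan's own biology, ER can also rise in ER-positive tumours that contain an ER-low subpopulation.
- *Percent change would be computed on three categories.* Section 9.2.2.3 also describes quantitative image analysis, 17.3 records percent staining, and the categories have their own use in 17.4.3.
- *A third of patients cannot be used for CTCs.* The statement "At least two-thirds of patients with metastatic breast cancer have >1 CTC per 7.5 mL blood" is a general figure for one platform. Section 9.1.2 adds a second that does not rely on EpCAM. A patient with no baseline CTC has no expression value on any measure.

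Section 17.4.4 does not say that the change is relative to baseline, so percentage points are a possible reading. Section 17.4.5, with "from pre-treatment levels will be determined for each patient", points to relative change. This ambiguity is itself a reason to state the measure. It is also fair that assessing change can be met descriptively, but Section 17 plans no descriptive summary of tissue change either.

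The limits on importance stand: the work is correlative or exploratory, and no primary endpoint or treatment decision depends on it.

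**Conclusion.** The point holds within limits. On the relative reading that Section 17.4.5 indicates, the measure is undefined at 0% baseline ER and strongly baseline-dependent at 1 to 9.9%. About 4 to 8 patients per arm are in that range, given the plan's 10% to 20% figures and 90% usable tissue; how many are at exactly 0% is unknown.

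In 17.4.4 the harm is loss of the 0% patients and some re-ranking. It is modest, and its simulated size rests on the assumed restoration signal. In 17.4.5 extreme values enter the Bland-Altman limits directly, and weighted kappa has no categories to work on.

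The firmer part is independent of the measure and of these assumptions: objectives 2.3.1 and 2.3.2 have no estimate or test of change.

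**What to change.** 1. In 17.4.4 and 17.4.5, replace percent change with absolute change: percentage points of positive cells, or the continuous image-analysis score, recorded under 9.2.2.3.
2. Add, per arm and marker, a paired estimate of change from baseline to the end of Cycle 1 with a Wilcoxon signed-rank test, labelled exploratory and without multiplicity control.
3. In the ER <10% stratum, show ER change and the number converting from <10% to ≥10%. Interpret ER change in Arm 2 in light of fulvestrant's down-regulation of the receptor (8.2.1).
4. Limit CTC change to patients with evaluable CTCs at both times, and report how many are not evaluable.
5. Use weighted kappa only on ordinal categories defined for both tissue and CTCs; 9.2.2.3 defines them for tissue only.

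Cost: SAP wording, a CTC category scale and retention of the continuous score, with the same specimens and assays. Downsides: more exploratory tests, and a ceiling on absolute change at high baseline (a patient at 90% can gain at most 10 points).

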### 17.4.5 Examination of changes in blood biomarkers after one cycle of initial treatment

At the end of Cycle 1, the percent change in CTC expression of Aurora A kinase, ER, and phospho- SOX2 expression from pre-treatment levels will be determined for each patient.

Bland-Altman plots and weighted kappa statistics will be used to examine the concordance between the percent change in Aurora A kinase, ER, and phospho-SOX2 expression from pre-treatment levels in CTC and in tumor tissue.

A plot of the percent change expression of Aurora A kinase, ER, and phospho-SOX2 expression from pre-treatment levels in CTCs and that in tissue will be constructed with using different symbols for each type of clinical response (CR, PR, SD or PD) to visually assess for trends.

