**NOTE: Xenografting will only be done for patients who enroll at Mayo Clinic in Rochester, Minnesota.**
- 2.4.2 After the first cycle of treatment, to assess changes in Aurora A kinase, p~SOX2 and ER expression on circulating tumor cells (CTCs), and to assess concordance between change in expression with tumor tissue and CTCs.

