CTCs vary in the degree of EpCAM expression, so malignant cells in the circulation may be missed by the CellSearch technology. Toward that end, other methodologies that do not rely on EpCAM for capture are now available. Therefore, a second 10 mL blood sample will be collected in the AccuCyte® Blood Collection Tube for CTC isolation using the AccuCyte® Platform (RareCyte; Seattle, WA). The blood collection tube contains an optimized preservative that stabilizes cells for up to 96 hours at ambient temperature. The AccuCyte® Platform [REDACTED] is a comprehensive, reproducible, and highly sensitive platform for enriching, identifying, and isolating CTCs for downstream molecular analyses (ref: Campton DE et al. BMC Cancer 2015. 15:360.). The system relies on density gradient centrifugation and allows for virtually complete harvesting of the buffy coat into a small volume for application to a microscopic slide without cell lysis or washing. Immunofluorescent staining for selected markers (e.g., cytokeratins, EpCAM, DAPI, CD45, HER2, ER, Aurora A kinase, p-SMAD5, and p-SOX2) is used for the efficient positive and negative identification of CTCs via automated scanning digital microscopy and image analysis. An integrated device provides for mechanically precise CTC retrieval for advanced genomic analyses, including next generation sequencing, on single or pooled CTCs.

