### 17.4.3 Examination of baseline and 4 week on initial treatment tumor biopsy specimens

Spearman rank correlation coefficient will be used to examine the association between ER $\alpha$  expression and the biomarkers: CD44, CD24, total and phosphorylated expression of AURKA, SMAD5, and SOX2 at baseline. Assuming that 90% of the 90 patients enrolled onto this trial will have sufficient baseline tissue to complete these analyses; there will be 81 patients will data available for these analyses. With a sample size of 81, a two-sided alpha=0.05 test of Spearman rank correlation coefficient will have a 90% chance of rejecting the true correlation is 0 when the true correlation is 35% or more.

A two sample test of the difference in proportions will be used to examine whether weak or no phosphorylated expression of AURKA, SMAD5, and SOX2 after one cycle of alisertib is associated with clinical benefit (CR +PR + SD on treatment for at least 6 months). The clinical response rate in ER+ MBC with single agent alisertib was reported to be 54%. As such we will assume that approximately 50% of the patients enrolled onto each treatment arm will have a documented clinical response. If, in a given treatment arm, 20 patients have a clinical response and 20 patients do not, a two sided alpha=0.05 test of the difference in two independent proportions will have at least an 85% chance of detecting a difference of 45% between the percentage of patients with a no or little expression of the biomarker among those who had clinical benefit and the percentage of patients with a no or little expression of the biomarker among those who did not have clinical benefit when the true percentage of patients with a no or little expression of the biomarker among those who did not have clinical benefit is 10% (or 20% or 25%).

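### Section 17.4.5 applies weighted kappa to a percent change with no categories or weights, and promises a CTC marker change for every patient although it exists only where cells are found at both draws

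*Combined protocol and SAP*

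**What the plan says.** Objective 2.4.2 is exploratory. It looks at marker change on CTCs after the first cycle and aims "to assess concordance between change in expression with tumor tissue and CTCs".

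Section 17.4.5 turns this into three steps. The percent change in three CTC markers "from pre-treatment levels will be determined for each patient". Then "Bland-Altman plots and weighted kappa statistics will be used to examine the concordance between the percent change in Aurora A kinase, ER, and" phospho-SOX2, comparing CTCs with tumor tissue. Finally, CTC change is plotted against tissue change, with a different symbol for each type of response.

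Three other places bear on this:

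- Section 9.1.2 gives the only detection figure, for CellSearch: "At least two-thirds of patients with metastatic breast cancer have >1 CTC per 7.5 mL blood assayed with this technology". It also explains why a second tube is drawn for the AccuCyte platform: "CTCs vary in the degree of EpCAM expression, so malignant cells in the circulation may be missed by the CellSearch technology". No detection rate is given for AccuCyte.
- Section 9.2.2.3 describes the tissue scale: "The intensity of biomarkers expression will be scored as strong, moderate, or weak-to-none using digital image analysis".
- Section 9.1.1 and the test schedules in Section 11 place a CTC draw before treatment and another at the end of Cycle 1.

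Section 17.4.5 states no sample size, power or precision, and does not say which platform supplies the data.

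**The concern.** There are two separate problems.

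The first is the statistic. Weighted kappa measures agreement between two ratings on the same ordered categories. Section 17.4.5 applies it to a continuous percent change and defines neither categories nor weights. Someone will have to choose them, and nothing in the plan requires that choice to be made before the data are seen. The reported agreement would then partly reflect the choice.

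The second is the set of patients. Marker expression is scored on captured cells. A patient with no CTC at baseline, or none at the end of Cycle 1, has no change to compute. The plan gives no rule for such patients, no minimum cell count and no requirement to report how many are left. Patients whose CTCs clear during Cycle 1 drop out of both the concordance analysis and the response-coded plot, and a reader of that plot would not see that they are missing.

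At stake is how objective 2.4.2 is interpreted. The primary endpoint is not affected.

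**Working it through.** The plan states no figure for this analysis, so there is none to reproduce.

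**1. What weighted kappa requires.** With k ordered categories,

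kappa_w = 1 − (Σ w_ij p_ij) / (Σ w_ij p_i. p_.j), where w_ij = (|i − j|/(k − 1))^m, with m = 1 for linear and m = 2 for quadratic weights.

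The inputs needed are k, the cut points and m. Section 17.4.5 supplies none of them. The three levels in Section 9.2.2.3 are levels of tissue staining intensity. They are not levels of change, and they are not stated for CTCs.

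**2. How much the choice can matter.** Illustration with assumed inputs: 400,000 pairs of percent changes, bivariate normal, mean −30 and SD 40 in both CTCs and tissue, correlation 0.6.

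| Cut points (%) | Linear | Quadratic |
|---|---|---|
| 0 | 0.38 | 0.38 |
| −50, +50 | 0.38 | 0.41 |
| −10, +10 | 0.38 | 0.44 |
| −25, +25 | 0.38 | 0.47 |
| −50, 0 | 0.39 | 0.50 |
| −75, −50, −25, 0, +25 | 0.38 | 0.57 |

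The data are the same in every row. With linear weights kappa barely moves. With quadratic weights it runs from 0.38 to 0.57, and from 0.41 to 0.50 across three-category choices alone. A second set of assumptions (correlation 0.5, mean −20, SD 50) gave 0.31 to 0.45 across category numbers and weights.

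The concordance correlation for the first set needs no cut points: 2 × 0.6 × 40 × 40 / (40² + 40² + 0²) = 1920/3200 = 0.60.

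The normal model is rough. It puts values below −100% at z = (−100 + 30)/40 = −1.75, about 4% of the distribution, which is impossible for expression. The table shows sensitivity to the choice; it does not forecast this trial's result.

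**3. How many patients have a change to analyse.** Patients with a change = 90 × P(CTCs at baseline) × P(CTCs still present at end of Cycle 1).

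- 90 patients: Section 17.4.3.
- Baseline detection 2/3: Section 9.1.2, the stated minimum for more than 1 CTC on CellSearch. Hence 90 × 2/3 = 60, leaving at most 30 with 0 or 1 cell.
- Persistence: not in the documents; assumed 40% to 100%.
- Paired tissue: Section 17.4.3 assumes 90% at baseline. The same 90% is assumed here for the second biopsy, so 0.9 × 0.9 = 0.81.

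| Persistence (assumed) | CTC change, of 90 | With paired tissue (× 0.81) |
|---|---|---|
| 100% | 60 | 49 |
| 80% | 48 | 39 |
| 60% | 36 | 29 |
| 40% | 24 | 19 |

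If AccuCyte raised baseline detection to 90% (assumption), the middle column would run from 81 down to 32 and the last from 66 down to 26.

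The first table leans low at baseline: two-thirds is a minimum, and a patient with exactly one CTC has a cell that can be scored.

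**The case against.** The best reply is that promising a change for each patient is ordinary shorthand for each evaluable patient, and that most of the section works on that reading. This stands in part. The Bland-Altman plots and the response-coded scatter can be drawn for patients with CTCs at both draws, provided CTC and tissue expression share a numeric scale. Section 17.4.4 already speaks of change in Aurora A-expressing cells in tissue, so such a scale is within reach. A reader might infer that the whole CTC analysis cannot be run; the documents do not support that. What cannot be run is kappa, and what cannot be met is the literal coverage of every patient.

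A second reply is that the protocol anticipated missed cells and added AccuCyte, which does not depend on EpCAM for capture. This also stands, and it is why one-third is only an upper bound. But no yield is given, and a second platform supplies no rule for patients in whom neither method finds cells.

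A third reply is that concordance can only ever be assessed where both values exist, so the restriction is built into the objective. That is right, and no method removes it. It still has to be visible.

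A reader might go further and infer that responders are largely missing, or that concordance is mainly measured in patients whose disease persists. The documents do not show this. Section 9.1.2 links counts relative to a threshold of 5 per 7.5 mL with outcome; it says nothing about clearance after one cycle, and no persistence rate is given. Selection by response is plausible, but its size is unknown.

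Finally, Bland-Altman plots already address agreement on the continuous scale. That is true, but they do not give a defined meaning to the kappa that Section 17.4.5 also promises.

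**Conclusion.** The point holds in a limited form. Weighted kappa on percent change is undefined as written, because Section 17.4.5 gives no categories and no weights. Under the illustrative assumptions, the unmade choices move a quadratic-weighted value between 0.38 and 0.57.

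Coverage of every patient cannot be assured. On CellSearch alone, up to about one-third may have 0 or 1 CTC at baseline, and those whose CTCs clear are lost in addition. At two-thirds baseline detection, 24 to 60 of 90 would have a CTC change for assumed persistence of 40% to 100%. Only the two-thirds and the 90 come from the documents.

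Nothing here supports a statement about the amount or direction of bias in the concordance estimate. This is a cheap improvement to an exploratory analysis, with no bearing on the primary comparison.

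**What to change.** Amend Section 17.4.5 before the marker data are analysed:

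1. Replace weighted kappa on percent change with a concordance (or intraclass) correlation coefficient and its confidence interval, reported beside the Bland-Altman plot. Put CTC and tissue on one numeric scale, such as the percentage of marker-positive cells. Keep weighted kappa only for ordered categories fixed in advance, with the weights stated.
2. Define the analysis set as patients with a pre-stated minimum CTC count at both draws on a named platform, and report how many qualify.
3. For all patients with both draws, tabulate CTC status (never detected, cleared, persistent, newly detected) against response. This will not remove the restriction, but it shows who is left out of the concordance analysis and the plot.

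The cost is SAP wording and one extra table; the planned samples suffice. The downside is that the evaluable set for concordance becomes explicit and smaller than all patients. No stated sample size changes, because the section states none.
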